5.3.2 Method of Analysis

5.3.2.1 Considerations for base MMRM model for change from baseline analyses

A mixed model with repeated measures (MMRM) will be used to analyze changes from baseline in a parameter of interest using fixed effects of LTE treatment group, visit (categorical), LTE treatment group-by-visit interaction, baseline of the parameter of interest, baseline of the parameter of interest-by-visit interaction, region (Japan and Australia will be combined), baseline MMSE, baseline disease stage, and baseline AD symptomatic medication use. The correlation between repeated measures of the outcomes will be taken into consideration. An unstructured covariance matrix will be used to model the within-subject variance-covariance errors. If the unstructured covariance structure matrix results in a lack of convergence, the heterogeneous first-order autoregressive covariance structure followed by the heterogeneous Toeplitz covariance structure will be used. The least-squares (LS) means, the differences in LS means between each LTE treatment group versus placebo at each visit, 95% confidence intervals (CIs), and p-values will be presented. In the primary analysis of each endpoint, missing data are assumed to be missing at random [Rubin 1976].

For the LTE interim analysis at PC DBL, only records up to week 104 will be included in the MMRM model.

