9.2. Randomization

Participants will be randomized on Study Day 1 after all screening and baseline assessments have been completed and after the Investigator has verified that the participants are eligible per criteria in Sections 8.1 and 8.2. Participants will be assigned a unique identification number that will be used on study-related documents pertaining to the participant. Any participant identification numbers that are assigned will not be reused even if the participant does not receive treatment. Rescreened participants will be assigned a new number.

Randomization will be stratified by [REDACTED], region, disease stage (MCI or mild AD), and baseline AD medication use. [REDACTED]

[REDACTED]

[REDACTED]

CONFIDENTIAL

The information contained herein may not be used, disclosed, or published without the written consent of Biogen MA Inc.

[REDACTED]

[REDACTED]

[REDACTED]

Participants who are participating in the LTE period and who were randomized to receive placebo during the placebo-controlled period will receive BIIB092 at the high dose (2000 mg) once every 4 weeks during the LTE period. Participants who were randomized to receive BIIB092 during the placebo-controlled period will continue to receive BIIB092 at the dose they were randomly assigned.

See the Study Reference Guide for details on randomization.

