16.4.2. Methods of Analysis

16.4.2.1. Analysis of Primary Efficacy Endpoint (Clinical Dementia Rating Scale – Sum of Boxes)

The CDR-SB is the primary efficacy endpoint. The population for the analysis of CDR-SB will be participants in the ITT population who have a baseline and at least 1 postbaseline CDR-SB score.

A mixed model with repeated measures (MMRM) will be used to analyze changes from Baseline in CDR-SB using fixed effects of treatment, time, treatment-by-time interaction, baseline CDR-SB, baseline CDR-SB-by-time interaction, region, disease stage (MCI versus mild AD), and baseline AD medication use. The correlation between repeated measures of the outcomes will be taken into consideration. The least-squares (LS) means, the differences in LS means between each treatment group versus placebo at Weeks 24, 52, and 78, 95% confidence intervals (CIs), and p-values will be presented. Changes from baseline in CDR subscores will be analyzed in a similar model. Additional details will be provided in the SAP.

The multiple comparison procedure modelling (MCP-MOD) method will be used to assess and model dose-response relationships (potential candidate models will include linear, linear-log, quadratic, maximum response [E_{max}], and logistic models as specified in Section 16.10) while controlling for multiplicity. The dose-response parameter of interest for MCP-MOD will be the LS means at Week 78 for each dose group from the mixed-effects model. Pairwise comparisons of each BIIB092 dose group versus placebo will also be conducted.

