16.4.2.2. Analysis of Exploratory Clinical Endpoints

The clinical endpoints assessing AD progression from Baseline include the results of the MMSE, ISLT, DKEFS, DSST, Trails A, eCog, ADCS-ADL, FAQ, ADAS-Cog 13, and NPI-10.

These clinical endpoints will be analyzed using data from participants in the ITT population who have a baseline and at least 1 postbaseline score for the specific endpoint being analyzed. As these are exploratory endpoints in this study, no additional multiplicity adjustment procedures will be applied to the analyses of these endpoints.

An MMRM approach will be used to analyze changes from baseline using fixed effects of treatment, time, treatment-by-time interaction, baseline score, baseline score-by-time interaction, region, disease stage (MCI versus mild AD), and baseline AD medication use. The correlation between repeated measures of the outcomes will be taken into consideration. The LS means, the differences in LS means between each treatment group versus placebo at Weeks 24, 52, and 78, and the 95% CIs and p-values will be presented.

Exploratory analysis may be performed to develop a composite cognitive score participants with MCI due to AD and/or participants with mild AD.

CONFIDENTIAL

The information contained herein may not be used, disclosed, or published without the written consent of Biogen MA Inc.

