2.3 Study Design

This is a Phase 2, randomized, double-blind, placebo-controlled, parallel-group study consisting of a double-blind, placebo-controlled period and an LTE period.

The study includes 2 substudies to address exploratory study objectives: a tau PET substudy and a CSF sampling substudy. The tau PET substudy is mandatory at study sites that have access to the ¹⁸F-MK6240 PET radioligand and have the capability to perform ¹⁸F-MK6240 PET scans. During the placebo-controlled period, the CSF sampling substudy is mandatory at all study sites that do not have access to the ¹⁸F-MK6240 PET radioligand. Participants will provide consent during Screening to participate in at least 1 of these substudies during the placebo-controlled period. Participants enrolled in the LTE period and who are participating in the tau PET substudy are required to continue participation in the tau PET substudy. Participation in the CSF sampling substudy during the LTE will be optional for all study participants, although participation is encouraged.

This study will be conducted in participants aged 50 to 80 years, inclusive, with MCI due to AD or mild AD according to National Institute on Aging-Alzheimer's Association criteria. Participants must have amyloid beta positivity confirmed at Screening by either CSF sampling or an amyloid PET scan. Participants must also perform at least 1 standard deviation below the age-adjusted normative mean on either the ISLT or the International Shopping List Test Delayed Recall and have a CDR global score of 0.5 for MCI due to AD or 0.5 or 1 for mild AD, an MMSE score of 22 to 30 (inclusive), and a CDR Memory Box score of ≥ 0.5 .

During the dose-blinded LTE period, participants will receive BIIB092 by IV once every 4 weeks beginning at Week 80. Participants who were randomized to receive BIIB092 during the placebo-controlled period will continue to receive BIIB092 at the dose they were randomly assigned. Participants randomized to receive placebo during the placebo-controlled period will receive BIIB092 at the high dose (2000 mg) once every 4 weeks during the LTE period.

The total duration for participants who complete the placebo-controlled period and do not enter the LTE period will be approximately 99 weeks. For participants who complete both the placebo-controlled period and the LTE period, the total study duration will be approximately 247 weeks.

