3.6 Stratification Factors and Subgroup Variables

Stratification factors are:

- Tau PET/CSF sampling substudy enrollment (If subjects enrolled in both substudies, subjects will be counted as tau PET substudy)
- Region (US, Australia, Japan, EU < EU countries include France, Germany, Italy, Spain, and Sweden >, Poland)
- Baseline disease stage (MCI or mild AD)
- Baseline AD symptomatic medication use (Yes/No)

All stratification factors are based on subjects' status at PC baseline. A comprehensive list of baseline AD symptomatic medication can be found in PC SAP.

No subgroup analyses will be conducted.

CONFIDENTIAL

The information contained herein may not be used, disclosed, or published without the written consent of Biogen MA Inc.

	Statistical Analysis Plan Long-Term Extension Period	V1.0
---	--	-------------

4 List of Planned Study Analyses

There are two milestone LTE analyses planned for this study: LTE analysis at PC period database lock and the final analysis. The final analysis, which is also known as End of LTE analysis, will only be performed when the LTE study is completed.

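### Minor, almost free: the LTE efficacy model adjusts for three of the four stratification factors and leaves out tau PET/CSF substudy enrolment

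*SAP*

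**What the plan says.** SAP 3.6 names four stratification factors: "Tau PET/CSF sampling substudy enrollment", region, baseline disease stage and baseline use of symptomatic AD medication. It also settles the coding of the first: "If subjects enrolled in both substudies, subjects will be counted as tau PET substudy".

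SAP 5.3.2.1 gives the base MMRM. Its fixed effects are LTE treatment group, visit, their interaction, the baseline value, "baseline of the parameter of interest-by-visit interaction", and then "region (Japan and Australia will be combined), baseline MMSE, baseline disease stage, and baseline AD symptomatic medication use". SAP 5.3.3 and 5.3.4 send CDR-SB and all the modelled exploratory endpoints to this model, so no other efficacy model supplies the missing factor.

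The protocol matches. Section 16.4.2.1 adjusts CDR-SB for "region, disease stage (MCI versus mild AD), and baseline AD medication use", and 16.4.2.2 uses the same three for the exploratory endpoints. Protocol 9.2 reads "Randomization will be stratified by [REDACTED], region, disease stage (MCI or mild AD), and baseline AD medication use"; the first factor is blacked out there and is known only from SAP 3.6. On how membership arises, SAP 2.3 says "The tau PET substudy is mandatory at study sites that have access to the" radioligand and can run the scans.

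**The concern.** Stratifying on a factor removes chance imbalance in it between arms. If the factor also predicts outcome, the treatment contrast varies less than it would under simple randomisation. A model that ignores the factor leaves the between-stratum variation in the residual, so it reports a standard error larger than the true one. Intervals are then a little too wide and the test rejects a little less often than its nominal level. The usual remedy is to analyse by the factors used to randomise. The plan does this for three factors (with Japan and Australia pooled within region) and gives no reason, in the text available, for dropping the fourth. At stake is agreement between the reported precision and the design, not the direction or validity of the treatment estimate.

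**Working it through.** **1. Count the factors.**

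| Factor (SAP 3.6) | Base MMRM (SAP 5.3.2.1) | Protocol MMRMs (16.4.2.1, 16.4.2.2) |
|---|---|---|
| Tau PET/CSF substudy | no | no |
| Region | yes, two regions pooled | yes |
| Disease stage | yes | yes |
| AD medication use | yes | yes |

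Four are stratified and three modelled.

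**2. Reproduce the plan's own figure.** Protocol 16.10 assumes a placebo change of 1.99, an SD of 2.38, a 40% reduction, 20% dropout and 176 per large arm.
- Difference: 0.40 × 1.99 = 0.796.
- Evaluable per arm: 176 × 0.8 = 140.8.
- SE: 2.38 × √(2/140.8) = 0.2837.
- Power: Φ(0.796/0.2837 − 1.96) = 80.1%, against the stated figure of approximately 80%.

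This is the pairwise high-dose comparison at Week 78. The plan's stated method is MCP-MOD, and it gives no power figure for the LTE.

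**3. Size of the excess in the reported SE.** Let a share f of participants be in one substudy, let the substudies differ by d points, and let S be the variance within substudy. With complete data, the model without the term estimates the variance as S + f(1−f)d². Accounting for the factor fully at that visit shrinks the reported SE by

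g = 1 − √[S / (S + f(1−f)d²)].

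*Assumed, because the documents do not give them:* f, d, and a random-slope variance pattern with measurement SD m of 0.7 or 1.0. Scaling the Week 78 SD to Week 104:
- m = 0.7: (2.38² − 0.49) × (104/78)² + 0.49 = 9.69, SD 3.11.
- m = 1.0: (2.38² − 1) × (104/78)² + 1 = 9.29, SD 3.05.

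Results at Week 104 (range over the two values of m):

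| d at Week 104 | g, f = 0.5 | g, f = 0.3 |
|---|---|---|
| 0.25 | 0.08% | 0.07% |
| 0.5 | 0.32–0.33% | 0.27–0.28% |
| 1.0 | 1.27–1.32% | 1.07–1.11% |

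For example, with d = 1.0, f = 0.5 and S = 9.29: 1 − √(9.29/9.54) = 1.32%. Allowing for dropout (95/88/80% observed at Weeks 24/52/78, then 50% or 75% at Week 104) widens the f = 0.5 ranges only to 0.28–0.33% and 1.12–1.32%.

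**4. Cross-check at Week 78.** A difference growing linearly to 1.0 at Week 104 is 0.75 at Week 78. With S = 2.38² = 5.664 and f = 0.5, f(1−f)d² = 0.141, so g = 1 − √(5.664/5.805) = 1.2%. A full 1.0 point already present at Week 78 would give 2.1%.

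**5. Error rate without the term.** 2 × [1 − Φ(1.96/(1−g))] gives 4.9% for g = 0.28% and 4.7% for g = 1.32%, against a nominal 5%.

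**6. What a main effect recovers.** If the difference is constant from Week 24, a main effect recovers all of the excess: 0.32–0.41% for 0.5 points and 1.27–1.53% for 1.0 point, over the same dropout patterns. If the difference grows linearly, it recovers only 0.05–0.10% and 0.21–0.40%; the rest would need a by-visit term.

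**7. Effect on the estimate.** In 6,000 simulated trials per setting (654 participants, 1:1:2:2, blocks of 6 within substudy, block size assumed), with d = 0, 0.5 or 1.0 and no true treatment effect, the mean Week 104 contrast was between −0.004 and 0.005 with and without a substudy-by-visit term (Monte Carlo SE about 0.004). The ratio of empirical SEs, with versus without the term, was 0.9999 to 1.0001. The term changes the reported SE and leaves the estimate alone.

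**The case against.** The strongest reply is that nothing depends on this. The LTE efficacy endpoints are exploratory (SAP 2.2), the error is on the conservative side, and every input that sets its size is assumed. Membership follows site access to the tracer, so region may already absorb most of any difference, and the calculation uses an SD not reduced for baseline CDR-SB, MMSE, stage or medication. All of that stands, and it is why the point is minor.

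The first factor is redacted in the protocol, and the placebo-controlled SAP, to which this SAP often defers, is not available. A reason for the omission may exist elsewhere. That limits what can be said about intent, but it does not put the term in the stated model.

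Three stronger readings are tempting and not supported:
- *That the SAP departs from the protocol.* Both leave the factor out.
- *That adjustment would buy precision worth extra participants.* The empirical SE does not change, because stratification has already secured the balance.
- *That a substudy-by-visit interaction is required.* Region, stage and medication all enter as main effects only, and the argument that prognostic gaps widen over time applies at least as well to stage. The one by-visit covariate in the model is the outcome's own baseline.

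**Conclusion.** The omission is verifiable from SAP 3.6 and 5.3.2.1 and is worth correcting as a minor improvement. It does not bias the early-start versus late-start contrast, does not inflate the type I error, and leaves the point estimate essentially as it is. If substudy enrolment is prognostic, reported standard errors and intervals are slightly too wide: about 0.3% for an assumed 0.5-point difference at Week 104 and about 1% for an assumed 1.0 point, with possibly nothing left once region and baseline scores are in the model. One point is a deliberately large assumption, about half of the 1.99-point placebo decline planned for Week 78; no source in the documents supports any particular value. A reader might infer that the LTE results are unreliable without the term; the figures do not support that. The case for change is consistency between randomisation and analysis, at negligible cost.

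**What to change.** In SAP 5.3.2.1, add substudy enrolment (tau PET versus CSF, coded as in SAP 3.6) as a fixed main effect, entered the same way as region, disease stage and AD medication use. If it is left out on purpose, one sentence giving the reason would do instead.

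The cost is one degree of freedom per model, with no new data, visits or participants. Because the LTE models reuse placebo-controlled data, check whether the placebo-controlled SAP carries the term. If it does not, note that contrasts up to Week 78 will come from slightly different covariate sets in the two reports.

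A substudy-by-visit term is optional, as a sensitivity analysis only. It uses one degree of freedom per post-baseline visit (SAP Appendix I, Table 1): 4 for CDR-SB at the interim, and in the final models up to 9 for CDR-SB and up to 12 for MMSE.

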16.10. Sample Size Considerations

There was no formal sample size calculation for the primary endpoint of safety.

The planned sample size is 528 participants, randomized in a 1:1:2:2 ratio, with 88 participants assigned to the BIIB092 low-dose group (44 assigned to 125 mg once every 4 weeks and 44 assigned to 375 mg once every 12 weeks), 88 participants assigned to the medium-dose group (600 mg once every 4 weeks), 176 participants assigned to the high-dose group (2000 mg once every 4 weeks), and 176 participants assigned to the placebo group. This sample size provides approximately 80% power to detect a dose-response relationship in the change from baseline in CDR-SB (primary efficacy endpoint) at 18 months (Week 78), assuming a mean change of 1.99 from baseline in CDR-SB at 18 months in the placebo group and a common SD of 2.38, a maximal 40% reduction for the highest BIIB092 dose group compared with the placebo group, and an estimated 20% dropout rate at 18 months (Week 78) in this study. Six different dose-response relationships will be tested at the 2-sided 5% significance level, using the MCP-MOD method to control for multiplicity [Bretz 2005]. Optimal contrasts will be constructed to detect potential dose-response trends under common dose-response curves (e.g., Emax, exponential, logistic, linear in log dose, and quadratic model) which are illustrated with the parameters shown in Figure 2.

The mean and SD of the change from baseline in CDR-SB at 18 months for the placebo group is based on available Alzheimer’s Disease Neuroimaging Initiative (ADNI) data from ADNI 1, ADNI 2, and [REDACTED].

[REDACTED]

[REDACTED]

[figure not shown]
[REDACTED]

CONFIDENTIAL

The information contained herein may not be used, disclosed, or published without the written consent of Biogen MA Inc.

In the LTE period, the actual sample size, [REDACTED], is dependent on the enrollment rate, and thus, sample size calculation is not needed.

Figure 2: Dose-Response Shapes Based on Clinical Dementia Rating Scale – Sum of Boxes Mean Change from Baseline at Week 78

ED₅₀ = median effective dose; Emax = maximum response

Note: This figure was generated using ADDPLAN[®] DF Version 3.1.8, by Aptiv solutions.

CONFIDENTIAL

The information contained herein may not be used, disclosed, or published without the written consent of Biogen MA Inc.

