C-SSRS	Columbia Suicide Severity Rating Scale
CV	coefficient of variation
DKEFS	Delis-Kaplan Executive Function System
DSST	Digit Symbol Substitution Test
ECG	electrocardiogram
EMACC	Early AD/ MCI Alzheimer's Cognitive Composite
E _{max}	Maximum response
EOS	End of study
EOT	End of treatment
ET	Early termination
FAQ	Functional Activities Questionnaire
FAS	Full Analysis Set
eCOG	Everyday Cognition
ICH	International Conference on Harmonisation
INR	Prothrombin Intl. Normalized Ratio
IRT	interactive response technology
iADRS	The Integrated Alzheimer's Disease Rating Scale
LS	Lease Square Mean
ISLR	International Shopping List Test Delayed Recall
ISLT	International Shopping List Test Immediate Recall
LLOQ	lower limit of quantification
LTE	long-term extension
LP	Lumbar puncture
MA	macrohemorrhages
MCI	mild cognitive impairment

CONFIDENTIAL

The information contained herein may not be used, disclosed, or published without the written consent of Biogen MA Inc.

MedDRA	Medical Dictionary for Regulatory Activities
mH	microhemorrhages
MMRM	mixed-model repeated measures
MMSE	Mini-Mental State Examination ³
MRI	magnetic resonance imaging
NPI-10	Neuropsychiatric Inventory-10
PC	Placebo control
PCP	Placebo control period
PCS	potentially clinically significant
PD	Pharmacodynamics(s)
PET	positron emission tomography
PLS	Partial least squares
PK	pharmacokinetic(s)
PT	Preferred term
PT	Prothrombin Time
QoL-AD	Quality of Life for Alzheimer's Disease
QTcF	Corrected QT interval by Fredericia
ROI	region of interest
RUD-Lite	Resource Utilization in Dementia – Lite Version
SAE	serious adverse event
SAP	statistical analysis plan
SD	standard deviation
SOC	System organ class
SS	superficial siderosis
SUVr	standard uptake value ratio
TEAE	treatment-emergent adverse event
TIV	Total Intracranial Volume
Trails A	Trail Making Test, Part A
ULN	upper limit of normal
VE	vasogenic edema
WHO	World Health Organization
ZBI	Zarit Burden Interview

1 Introduction

This statistical analysis plan (SAP) covers the analyses of the LTE period and the analyses across both the placebo-controlled period and the LTE period of the study, 251AD201. A separate SAP has been prepared for the analyses of the placebo-controlled period.

Unless stated otherwise, all statistical tests will be 2-sided with statistical significance level of 0.05.

The statistical software, SAS[®] will be used for all summaries and analyses.

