5.6.2 Structural MRI Analysis

No subjects reached week 226, the primary analysis timepoint for structural MRI. Therefore, structural MRI is not reported or statistically analyzed for the LTE period.

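### The MMRM covariance fallback tries heterogeneous AR(1) before the heterogeneous Toeplitz structure that contains it, and names no robust standard error for either

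*SAP*

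**What the plan says.** SAP 5.3.2.1 defines one base MMRM for the change-from-baseline analyses, and SAP 5.3.3 and 5.3.4 apply it to CDR-SB and to the exploratory scales. Unstructured covariance is the first choice. If it does not converge, "the heterogeneous first-order autoregressive covariance structure followed by the heterogeneous Toeplitz covariance structure will be used". The section promises confidence intervals and p-values at each visit and assumes data are missing at random. It does not say whether standard errors are model-based or empirical, and it gives no degrees-of-freedom method. It also does not say what moves the analyst from the first fallback to the second; failure of the first is the natural reading.

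The SAP Introduction states that "all statistical tests will be 2-sided with statistical significance level of 0.05" unless stated otherwise. The LTE interim model uses records up to Week 104 only (SAP 5.3.2.1). At final analysis SAP 5.3.3 leaves the week of interest open. SAP 5.6.2 reports that "No subjects reached week 226, the primary analysis timepoint for structural MRI", while Appendix I, Table 1 still lists a Week 226 window for every efficacy scale.

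**The concern.** A fallback sequence should give up generality a step at a time: unstructured, then the most general structure that converges, then simpler ones. Here the more restrictive structure comes first. Any data set that can support heterogeneous Toeplitz will nearly always support heterogeneous AR(1), so the second step is close to empty.

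Heterogeneous AR(1) ties the whole correlation matrix to one parameter and makes correlation decay geometrically with visit order. If repeated change scores do not behave that way, two things follow. Model-based standard errors no longer describe the real sampling variation. And because a likelihood analysis uses the covariance to carry information from observed to missing visits, a wrong covariance can bias late-visit means under MAR dropout. What is at stake is the interval, p-value and estimate for early-start against late-start high dose at LTE visits.

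**Working it through.** **1. The plan's own figure, which anchors the scale.** Protocol 16.10 gives the only figure that can be reproduced: "This sample size provides approximately 80% power to detect a dose-response relationship in the change from baseline in CDR-SB". Inputs: "The planned sample size is 528 participants, randomized in a 1:1:2:2 ratio" (176 each on high dose and placebo), "assuming a mean change of 1.99 from baseline in CDR-SB at 18 months in the placebo group and a common SD of 2.38", a high-dose effect equal to 40% of the placebo change, and 20% dropout.
- Difference = 0.40 x 1.99 = 0.796. Evaluable per arm = 176 x 0.8 = 140.8.
- SE = 2.38 x sqrt(2/140.8) = 0.2837. Ratio = 0.796/0.2837 = 2.806.
- Power = Phi(2.806 - 1.96) = 80.1%.

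The figure reproduces, so SD 2.38 at Week 78 is used below. Nothing in the documents supplies a within-participant correlation or an LTE retention rate.

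**2. Nesting.** For p visits, heterogeneous AR(1) has p + 1 parameters, heterogeneous Toeplitz 2p - 1, unstructured p(p+1)/2.

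| Model (visits from SAP Appendix I, Table 1) | p | AR(1) | Toeplitz | Unstructured |
|---|---|---|---|---|
| CDR, interim (Weeks 24, 52, 78, 104) | 4 | 5 | 7 | 10 |
| CDR, all windows except Week 226 | 8 | 9 | 15 | 36 |
| CDR, all windows | 9 | 10 | 17 | 45 |
| MMSE, interim | 7 | 8 | 13 | 28 |
| MMSE, all windows | 12 | 13 | 23 | 78 |

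Toeplitz lets each lag have its own correlation; AR(1) fixes the lag-k correlation at rho^k. MMSE visits are also 10 to 26 weeks apart, and order-based AR(1) gives every adjacent pair the same correlation.

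**3. Standard-error ratio under the fallback.** This is a large-sample calculation with monotone missingness unrelated to outcome. With share w_k of participants observed through visit k, true covariance S and working covariance V fitted by minimising the expected -2 log-likelihood:
- A = sum of w_k V_k^-1, and B = sum of w_k V_k^-1 S_k V_k^-1.
- Model-based variance is A^-1; true variance is A^-1 B A^-1. The ratio is the square root of their quotient at each visit.
- True size of a nominal 5% test = 2 Phi(-1.96 x ratio).

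Assumed true covariances: growth-type (random slope plus error with error SD 1.0 or 1.5, random slope with shared baseline error, Brownian plus error), compound symmetry (0.5, 0.7) and AR(1) 0.7. Growth-type cases have SD 2.38 at Week 78. Assumed retention is 80% at Week 78, then as shown.

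| Model and retention | Growth-type, AR(1) fitted | Compound symmetry, AR(1) fitted | Growth-type, Toeplitz fitted |
|---|---|---|---|
| Interim, Week 104, 78% observed | 0.915-0.953 | 1.01-1.02 | 0.92-0.95 |
| Interim, Week 104, 50% observed | 0.97-0.99 | 1.01-1.02 | 0.97-0.99 |
| Interim, Week 104, 20% observed | 1.04-1.08 | 1.00-1.01 | 1.04-1.09 |
| To Week 152 (70/50/30% observed): Week 104 | 0.88-0.93 | 1.01-1.02 | 0.90-0.93 |
| same: Week 128 | 0.87-0.93 | 1.01-1.03 | 0.89-0.93 |
| same: Week 152 | 0.97-0.99 | 1.02-1.05 | 0.94-0.98 |
| To Week 200 (65/45/30/15/5%): Week 128 | 0.86-0.92 | 1.01-1.04 | 0.87-0.92 |
| same: Week 200 | 1.10-1.22 | 1.02-1.05 | 1.09-1.18 |

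When AR(1) is true, every ratio is 1.00. Fitting Toeplitz to compound symmetry or AR(1) also gives 1.00. In test size, a ratio of 0.915 means 7.3%, 0.90 means 7.8%, 0.87 means 8.8% and 1.08 means 3.4%.

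**4. Bias in the means.** In a separate large-sample check with growth-type covariance and MAR dropout, the early-late difference at Week 152 was shrunk by 6-8% under heterogeneous AR(1) and by 2-3% under heterogeneous Toeplitz.

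**Limits.** Steps 3 and 4 are asymptotic. Step 3 omits covariates and was not checked by simulation.

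**The case against.** Four arguments on the other side have force.

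- **It is conditional and exploratory.** The LTE primary objective is safety (SAP 2.1), LTE efficacy endpoints are exploratory (SAP 2.2) without multiplicity adjustment (SAP 5.3.1), and Protocol 16.1 describes LTE efficacy evaluation as descriptive. The fallback matters only if the unstructured fit fails. At the interim, CDR has 4 visits and 10 covariance parameters with 654 randomized, and there is no evident reason for failure. This stands and sets the severity.
- **Late visits may hold little data.** Nobody reached Week 226, so at most 8 CDR visits can contribute. The exposure categories in SAP 5.2.4 stop at 26 infusions; 20 run through Week 76 and the next six fall at Weeks 80 to 100, which hints that follow-up ended near Week 104. That is an inference, but it makes the later-visit ratios less relevant.
- **Reordering does not repair the standard error.** This stands: the Toeplitz ratios under growth are close to the AR(1) ratios. The case for reordering is that Toeplitz contains AR(1), is exact whenever correlation depends only on lag, and leaves less bias in the means.
- **Sandwich errors are justified only in large samples.** This stands for very thin visits, where they can themselves be too small.

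A reader might infer from the nesting that LTE standard errors will be 10-20% too small and LTE p-values too small. The documents do not support that. It needs a correlation and a retention that they do not give. The sign changes across plausible settings, and no interim Week 104 setting reaches 10%. A reader might also take model-based errors to be the SAP's stated choice; they are an inference from its silence.

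**Conclusion.** The point holds as a minor one. The order of the fallback is stated in the text and runs from restrictive to general, so the Toeplitz step is almost never used, and no robust standard error is named.

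The effect on LTE standard errors depends on assumptions and can go either way. If errors are model-based and the true covariance is growth-type with good retention, they are roughly 5-10% too small at Week 104: 5-8.5% in the interim model, and up to 12% in one final-model setting. They are about 10-15% too small at some later visits. Under compound symmetry they are correct or up to about 5% too large. At a very thin last visit under growth they can be more clearly too large, up to 22% with 5% observed. None of these figures can be fixed from the documents.

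Non-convergence is mainly a concern for the final model with many sparse visits, and for scales with more visits than CDR.

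**What to change.** In SAP 5.3.2.1, reverse the fallback: heterogeneous Toeplitz if the unstructured matrix does not converge, then heterogeneous AR(1). Add that empirical (sandwich) standard errors will be used for any fit that is not unstructured, and say that non-convergence is what triggers each step.

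Both parts are needed: the order limits bias in the means, and the sandwich estimator corrects the standard error in large samples.

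The cost is one SAP sentence and one software option, with no new data. Intervals under the fallback may be somewhat wider, and results at visits with very few participants should be read with care because sandwich errors are unreliable there.
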